4. Treatment Phase: iTBS-TMS. Active iTBS-TMS Treatment Group – will receive a total of 20 treatments delivered 5 days/week, two treatments per day, over 2 consecutive weeks. Sham Treatment group will receive the same frequency and duration of treatment, without actual administration of iTBS-TMS. The majority of participants will be recruited from residential treatment programs; therefore, 24 hour monitoring for any adverse events will be in place as an additional layer of participant safety.

5. Post-Treatment Phase: Within 3-4 days of completion of the Treatment Phase, all participants will repeat neurocognitive assessment, select psychiatric assessment measures, select alcohol and substance questionnaires, 3 Tesla Magnetic Resonance Neuroimaging and blood draw. During this time, all participants will be receiving treatment-as-usual at the VA clinics, and scheduling of iTBS-TMS will be arranged as not to interfere with their daily curriculum.

6. Monthly Follow-ups: For the 6 months following completion of active/sham iTBS treatment, participants will be contacted monthly, via telephone or in person, to complete brief standardized measures of alcohol and substance use, as well as craving to assess for changes in these variables over the preceding 30 days. These brief contacts will be 15-20 min in duration and tracking sobriety is the primary outcome measure of this study..

DETAILS OF RECRUITMENT, DESIGN AND TREATMENT

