d) State if audio or video recording will occur. Describe what will become of the recording after use, e.g., shown at scientific meetings, erased. Describe the final disposition of the recordings.

N/A

e) Describe alternative procedures or courses of treatment, if any, that might be advantageous to the participant. Describe potential risks and benefits associated with these. Any standard treatment that is being withheld must be disclosed in the consent process and form. (i.e. standard-of-care drug, different interventional procedure, no procedure or treatment, palliative care, other research studies).

The participants in this study will concurrently receive standard-of-care cognitive-behavioral and pharmacological interventions from the VA Palo Alto substance treatment clinics they are enrolled in. There are no potential risks to the participants who receive concurrent cognitive-behavioral and any procedure associated with the proposed research protocol. No participant will be enrolled who is taking a medication that lowers seizure threshold. Risks to confidentiality will be minimized by following all procedures dictated by HIPAA and NIDA/NIAAA Certificate of Confidentiality. Of course, potential participants may decline to be involved in the study and receive only the available standard-of-care cognitive-behavioral and pharmacological interventions

Will it be possible to continue the more (most) appropriate therapy for the participant(s) after the conclusion of the study?

This study will not impose any restrictions on treatment/therapy after conclusion. At this point, the iTBS treatment under investigation will only be available during the treatment phase of the study.

g) Study Endpoint. What are the guidelines or end points by which you can evaluate the different treatments (i.e. study drug, device, procedure) during the study? If one proves to be clearly more effective than another (or others) during the course of a study, will the study be terminated before the projected total participant population has been enrolled? When will the study end if no important differences are detected?

In order to have sufficient power to evaluate the primary hypotheses of this study, it is expected to continue until all participants have completed the procedures and follow-up assessments.

3. Background

a) Describe past experimental and/or clinical findings leading to the formulation of the study.

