Screening information will only be used to determine eligibility for the study and to facilitate contact for study informed consent and enrollment purposes. Completed screening forms will be kept in a locked file cabinet in a locked office at the Palo Alto VA.

d) Please describe an adequate plan to destroy the identifiers at the earliest opportunity consistent with conduct of the research, unless there is a health or research justification for retaining the identifiers or such retention is otherwise required by law.

Per VA requirements, screening forms for participants deemed ineligible will be stored in a secure, locked file cabinet in a locked office, and disposed of 6 years after the study ends. In addition, participants will be notified of their eligibility status by study staff.

IRB approval of any project is for a maximum period of one year. For continuing projects and activities, it is the responsibility of the investigator(s) to resubmit the project to the IRB for review and re-approval prior to the end of the approval period. A Notice to Renew Protocol is sent to the Protocol Director 7 weeks prior to the expiration date of the protocol.

Department Chair must approve faculty and staff research that is not part of a sponsored project. VA applicants must have Division Chief or Ward Supervisor approval. E-mail the Department Chair approval to [contact].

Statistical Analyses Plan

Primary Hypothesis:

1a) Veterans who receive active iTBS-TMS treatment for AUD demonstrate a significantly lower frequency of relapse at 6 months following treatment than controls (i.e., Veterans with AUD who receive sham iTBS-TMS).

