Statistical Approach: Primary Hypothesis 1a will be tested with binary logistic regression. The criterion/dependent measure is relapse status (abstained or relapsed during the 6 months after last iTBS-TMS session). Treatment group (active iTBS-TMS vs. control) is the target predictor, and covariates will include age and composite neurocognitive functioning (based on demographically adjusted RBANS total score) as these variables may account for both within and between subject group variance. PTSD severity (based on PCL-5 total score), substance use severity (based on NIDA Drug Survey composite score), depression severity (based on BDI total score), and/or smoking severity (based on pack-years) will be considered as covariates if, after random assignment, there are post-hoc differences between treatment groups on these variables following breaking of the blind.

1b) Veterans who receive active iTBS-TMS treatment for AUD will demonstrate a significantly greater duration of abstinence in the 6 months following treatment than controls.

Statistical Approach: Primary Hypothesis 1b will be tested with Cox regression. The criterion/dependent measure is duration of abstinence after final iTBS-TMS session, and covariates include those listed for Primary Hypothesis 1a.

Secondary Hypothesis:

In the active iTBS-TMS group, Veterans with: (a) lower Glu concentration, (b) lower perfusion (blood flow), and (c) smaller volume of the left DLPFC at baseline will demonstrate a longer duration of abstinence over 6 months post treatment.

Confirmation of this hypothesis will indicate that participants who exhibit lower baseline Glu concentration, lower perfusion (blood flow), and/or smaller left DLPFC volume, and receive active iTBS-TMS, demonstrate the most robust iTBS-TMS treatment response because iTBS-TMS addresses these key neurobiological deficits that are associated with increased relapse risk. Confirmation of this hypothesis will advance our understanding of the neurobiological characteristics that predict the greatest benefit from iTBS-TMS at entry into treatment for AUD.

Statistical Approach: The Secondary Hypothesis will be tested with generalized linear mixed modeling or linear mixed modeling, depending on the distribution of the dependent measure. Duration of abstinence is the dependent measure.

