Neuroimaging measure (e.g., Glu level) and treatment group (active iTBS-TMS vs. control) are the target predictors, with age as a covariate because it will likely account for significant within and between subject variance. Smoking, PTSD and/or substance use severities will be used as covariates if there are post-hoc differences between treatment groups on these variables after random assignment. We predict an interaction between the specific neuroimaging measure (e.g., Glu level) and treatment group; follow-up simple effect tests will indicate that participants in the active iTBS-TMS group with lower Glu concentration,

lower perfusion (blood flow), and smaller volume of the left DLPFC at baseline will show the longest duration of abstinence. Separate models will be run for each neuroimaging predictor to minimize the risk of overfitting and corresponding inflated Type I error. To control significance levels of main effects and interactions for multiplicity of tests, we will employ a modified Bonferroni procedure described in our previous studies .

Exploratory Hypothesis 1

1a) Veterans with co-occurring MDD, who receive active iTBS-TMS, demonstrate a significantly lower frequency of relapse over 6 months following treatment than controls (i.e. Veterans with co-occurring MDD who receive sham iTBS-TMS).

Statistical Approach: Exploratory Hypothesis 1a will be tested with binary logistic regression. The criterion/dependent measure is relapse status (abstained or relapsed during the 6 months after last iTBS-TMS session). Treatment group (active iTBS-TMS vs. control) is the target predictor, with antidepressant use (binary, yes/no) as a covariate. Education and severity of PTSD, substance use, and/or depressive symptomatology will be considered as covariates if, after random assignment, there are post-hoc differences between treatment groups on these variables following breaking of the blind.

1b) Veterans with co-occurring MDD, who receive active iTBS-TMS, demonstrate significantly greater duration of abstinence in the 6 months following treatment than controls.

Statistical Approach: Exploratory Hypothesis 1b will be tested with Cox regression. The criterion/dependent measure is duration of abstinence after the final iTBS-TMS session. The target predictor and covariates include those for Exploratory Hypothesis 1a.

Exploratory Hypothesis 2

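### Two primary tests of the same relapse data have no alpha or success rule, and entry of four severity covariates stays open until after unblinding

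*Combined protocol and SAP*

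**What the plan says.** - **Primary Hypothesis 1a (Statistical Analyses Plan).** Veterans given active stimulation "demonstrate a significantly lower frequency of relapse at 6 months following treatment than controls". "Primary Hypothesis 1a will be tested with binary logistic regression".
- **Primary Hypothesis 1b.** The outcome is time abstinent after the last session. "Primary Hypothesis 1b will be tested with Cox regression", and its "covariates include those listed for Primary Hypothesis 1a".
- **Covariates for both.** Age and the RBANS total enter in any case. PTSD, substance use, depression and/or smoking severity "will be considered as covariates if, after random assignment, there are post-hoc differences between treatment groups on these variables following breaking of the blind". No test, effect measure or cutoff says what counts as a difference.
- **Secondary Hypothesis.** The parallel rule is firmer here: the "severities will be used as covariates if there are post-hoc differences between treatment groups". The plan's only multiplicity statement, a modified Bonferroni procedure, also stands in this section and refers to main effects and interactions.
- **Protocol body.** Section 2(g) Study Endpoint uses the plural: "In order to have sufficient power to evaluate the primary hypotheses of this study". Section 2(a), Monthly Follow-ups, names one outcome: "tracking sobriety is the primary outcome measure of this study". That phrase fits relapse status and duration of abstinence equally well.

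Neither the protocol nor the SAP gives an alpha, sidedness, an order of testing, an alpha split, or a rule on whether one or both primary tests must succeed.

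**The concern.** There are two gaps, and they compound.

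First, with complete follow-up the relapse indicator in 1a is the event indicator in 1b. The two tests will usually agree but not always. When they disagree, the plan does not say whether the trial succeeded.

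Second, whether each of four named severity scores enters the primary models is decided once treatment codes are known, against an undefined standard and in permissive wording. With about 24 relapses expected in 40 participants (40 × 0.60), adding or dropping a covariate can move a borderline p-value.

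At stake is whether a reader can tell what counts as a positive result and what error rate that claim carries. Section 3(a) Background expects VA clinicians to use the data in deciding about the treatment.

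**Working it through.** **Inputs from the documents.** 40 participants, 20 per arm (Section 2(a), Design); six months of follow-up (Section 2(a)); relapse of at least 60% within six months (Section 1(b), a background figure and not a design assumption); logistic and Cox models with age and RBANS fixed and four optional scores (SAP).

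**Assumptions.** Two-sided 0.05 per test; 60% relapse in both arms under no effect; exponential relapse times with complete follow-up over 182 days; Wald tests; three candidate cutoffs for a difference. The covariates are either non-prognostic or all have log HR 0.25 per SD, with severities independent or correlated 0.3. The main null runs used 10,000 trials per setting. The plan states no alpha, power or effect size, so it has no figure to reproduce.

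**Step 1. Ceiling for two tests.** If independent: 1 − 0.95² = 9.75%. Bonferroni sum: 10%. The tests are strongly correlated, so neither figure is realistic.

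**Step 2. Age and RBANS only.** P(either) = P(logistic) + P(Cox) − P(both). In one 2,500-trial run: 4.52 + 5.48 − 3.44 = 6.56%. In the main runs: logistic 4.4–5.0%, Cox 5.1–5.4%, both 3.0–3.5%, either 6.6–7.0%. A further run reached 7.2%, and other runs ranged from 6.3% to 7.6%. False claims of benefit on either test were 3.2–3.5% against a nominal 2.5%. The tests disagreed on significance in about 3–4% of null trials, and in about 7% under an assumed HR of 0.4.

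**Step 3. How often the trigger fires.** For four independent scores, the chance that at least one is flagged is 1 − (1 − a)⁴: 18.5% at a = 0.05, 34% at 0.10, 59% at 0.20. For a standardised difference of 0.2, SE = √(2/20) = 0.316 and z = 0.2/0.316 = 0.63, so p is about 0.53. Each score would cross that line by chance in about 53% of trials.

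**Step 4. Imbalance rule applied mechanically.** Entering exactly the scores past the cutoff gives 6.5–8.2% for either test across the three cutoffs, little above Step 2.

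**Step 5. Upper bound under discretion.** The analyst always takes the smallest p over subsets of the scores past the cutoff:

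| Assumed cutoff | Median covariate sets open | Either test | False benefit, either test | Logistic alone | Cox alone |
|---|---|---|---|---|---|
| p<0.05 | 1 | 7.3–7.9% | 3.6–3.8% | 4.9–5.3% | 5.8–6.1% |
| p<0.20 | 2 | 8.5–10.0% | 4.3–4.7% | 6.0–6.3% | 6.9–7.8% |
| standardised difference >0.2 | 4 | 10.8–14.0% | 5.3–6.8% | 7.5–8.2% | 8.8–11.3% |

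At 50% or 70% relapse, either test gives 6.6–7.4% with fixed covariates. The upper bound runs from 7.1–8.3% (p<0.05) to 10.4–15.3% (>0.2). Simulation error in the main runs is about 0.2–0.35 points.

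**Step 6. Power cost of locking age and RBANS.** Assume 60% relapse on sham and log HR = ln(ln 0.7 / ln 0.4) = ln(0.357/0.916) = −0.94, that is HR 0.39.
- At log HR 0.25 per SD or none, the mechanical rule changes logistic power by −2.8 to −0.2 points. It changes Cox power by −2.2 to +4.1 points in one set of runs, and by about +6 in another (37% locked, 43% with the >0.2 rule).
- At log HR 0.5 per SD, two runs gave Cox power of 25.1% locked against 36.8% with the >0.2 rule, and about 27% against 37%. Null error rose from 5.8% to 6.7%, so part of that gain is error inflation. At p<0.20 the gain is about 3 points. Logistic shows none.

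**The case against.** The strongest defence is that most of the analysis is already fixed: both model types, both outcomes, the treatment term, age, RBANS, and the four candidates with their scales. That stands. A reader might infer that the primary model is undefined, and the SAP does not support that. Only entry of four named scores is open.

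A reader might also infer that two primary tests double the error to about 10%. They do not, because the tests are highly correlated. Both hypotheses are directional, and with fixed covariates the excess in false benefit is about one point. With one named primary and a p<0.05 cutoff, even choosing the smallest p leaves 4.9–5.3% (logistic) or 5.8–6.1% (Cox).

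Nor is adjusting for imbalance itself at fault, since applied mechanically it adds little. Leaving all 16 covariate sets (2⁴) open in every trial would give 12.8% with non-prognostic scores and 18.8% at log HR 0.3 per SD. That ignores the plan's condition that the arms must differ: even at >0.2, all 16 sets are open in only 8.1–8.5% of trials. Nothing in the documents points to the >0.2 cutoff or to an intention to choose the smallest p.

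Finally, Section 3(a) calls the data preliminary, and Section 10(a) Benefits makes roll-out depend on replication. That limits the consequence. It does not answer the textual gap: no success rule exists, and the Bonferroni sentence belongs to the secondary hypothesis.

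**Conclusion.** The point holds in a limited form. The SAP makes 1a and 1b both primary without saying which decides or at what level, and it leaves entry of four severity scores to judgement after unblinding.

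Under the stated assumptions, success on either test with age and RBANS only carries about 6.6–7.2% error. Requiring both tests gives no inflation with fixed covariates, but the plan does not say which rule applies. Discretion over covariates takes the either-test figure to about 7–8% with a strict cutoff, and at most to about 11–14% with the loosest one considered. These are upper bounds and not forecasts of the error of a good-faith analysis.

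The omission is certain from the text. The sizes depend on the assumed alpha, relapse rate, cutoffs and prognostic strength.

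**What to change.** Before the blind is broken, amend the SAP as follows.

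1. State alpha and sidedness.
2. Name 1a or 1b as the single deciding test. Test the other only if the first is significant, or call it supportive.
3. Fix the covariates for 1a and 1b as age and baseline RBANS. The word baseline matters: Section 2(a) repeats neurocognitive testing after treatment, and the SAP does not date the score. Show adjustment for the four baseline severity scores as pre-listed sensitivity analyses, all reported.

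If the investigators prefer to keep an imbalance adjustment in the primary model, item 3 can instead write in the difference measure on baseline values, the cutoff, and mandatory entry when it is crossed. That is closer to the present plan and also removes the discretion.

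The cost is SAP wording, with no change to sample size, visits or data. A result significant only on the non-deciding test can no longer be called a primary success. Compared with a mechanical >0.2 rule, locking age and RBANS may lose roughly 0–6 points of Cox power if the severities have log HR 0.25 per SD, and about 10–12 points at 0.5 per SD, with little or no loss for logistic. The documents give no prognostic strength, so the investigators should weigh that range when choosing between the two options.

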
Additional Procedures for the Monitoring of Seizures and Suicidal Ideation/Behavior:

Screening, Baseline and Treatment Phase: In the unlikely event that a seizure does occur, participants will be closely monitored and treated for any medical or psychological consequences. rTMS sessions will be conducted at the VA Palo Alto MIRECC, which fully equipped to safely handle a seizure. If at any point during study participation, a participant has a seizure, the participant will be withdrawn from the study immediately (although they will still be followed for protocol assessments). All seizures will be considered serious adverse events (SAE) and as such, will be reported to the study PI. We will immediately suspend enrollment if 10 participants experience a seizure during study participation, and request that the Data Monitoring Committee (DMC) evaluate the SAE data, to determine if enrollment of new participants should be resumed without protocol changes, if protocol modifications should be made before resuming enrollment, or if the study should be terminated. We recognize that study termination or modification based on SAEs, such as seizures, ultimately rests with the DMC and the study PI.

If a participant expresses suicidal ideation/intent, and is determined to be a risk to self, a clinical evaluation will be immediately conducted by the PI (a licensed clinical psychologist), Co-Is (a licensed clinical psychologist or board certified psychiatrist), by the participant's individual mental health provider, and/or a mental health emergency clinician. The participant will remain with qualified study personnel or a MIRECC clinician until the evaluation has been completed and a decision made about disposition in conjunction with the Chief of Mental Health Outpatient Clinic or the emergency mental health clinician.

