2a) Cigarette smokers, who receive active iTBS-TMS, demonstrate a significantly lower frequency of relapse over 6 months following treatment than controls (i.e., Veterans with co-occurring smoking who receive sham iTBS-TMS).

Statistical Approach: Exploratory Hypothesis 2a will be tested with binary logistic regression. The criterion/dependent measure is relapse status (abstained or relapsed during the 6 months after last iTBS-TMS session). Treatment group (active iTBS-TMS vs. control) is the target predictor and with current pharmacotherapy for smoking cessation use (binary, yes/no) as a covariate. Education and severity of PTSD, substance use, and/or smoking severity (based on pack-years) will be considered as covariates if, after random assignment, there are post-hoc differences between treatment groups on these variables following breaking of the blind.

2b) Smokers, who receive active iTBS-TMS, demonstrate a significantly greater duration of abstinence over the 6 months following psychosocial treatment than controls.

Statistical Approach: Exploratory Hypothesis 2b will be tested with Cox regression. The criterion/dependent measure is duration of abstinence after final iTBS-TMS session. Treatment group is the target predictor and covariates include those for Exploratory Hypothesis 2a.

Tertiary Analyses

We will concurrently examine the associations between treatment group, multiple neurobiological, neurocognitive and clinical variables (and their potential interactions) and relapse status via an advanced multivariate dynamic longitudinal latent variable modeling framework. However, we are mindful of the proposed sample size, and will avoid building models that risk overparameterization and overfitting.

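### The Secondary Hypothesis models duration of abstinence with an LMM or GLMM that, as written, ignores censoring, although the SAP uses Cox regression for the same outcome elsewhere

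*Combined protocol and SAP*

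**What the plan says.** In the Statistical Analyses Plan, the Secondary Hypothesis holds that active-arm participants with lower glutamate, lower perfusion or smaller volume of the left DLPFC at baseline "will demonstrate a longer duration of abstinence over 6 months post treatment". The Statistical Approach reads: "The Secondary Hypothesis will be tested with generalized linear mixed modeling or linear mixed modeling, depending on the distribution of the dependent measure", and then "Duration of abstinence is the dependent measure". The target test is also named: "We predict an interaction between the specific neuroimaging measure (e.g., Glu level) and treatment group". Age is a covariate, each imaging measure has its own model, and a modified Bonferroni procedure handles multiplicity.

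For duration of abstinence after the last session, the same plan chooses a different model three times: "Primary Hypothesis 1b will be tested with Cox regression", "Exploratory Hypothesis 1b will be tested with Cox regression" and "Exploratory Hypothesis 2b will be tested with Cox regression". It gives no reason for departing from Cox in the Secondary Hypothesis. It names no repeated measure or random effect there, and does not say what duration is assigned to someone who has not relapsed by 6 months or who is lost to follow-up.

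**The concern.** Duration of abstinence over a fixed 6-month window is a time to relapse. For a participant who reaches 6 months without relapse, the plan knows only that the duration exceeds 6 months. For a participant lost at month 3, it knows only that the duration exceeds 3 months. Cox regression uses both facts correctly. A model that takes duration itself as the response must treat these values as exact or discard the participant. Choosing the model by the shape of the distribution does not help, because the pile-up at 6 months comes from follow-up ending.

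The stake is the plan's one named test of whether baseline imaging predicts who benefits. The stated model gives away power for that interaction even with full follow-up. With loss it also distorts the estimate, because a drop-out date is read as a relapse date.

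**Working it through.** **Inputs.** From the documents: 40 participants, 20 per arm (section 2(a), Design, Treatment Phase and Treatment Arms); 6 months of follow-up with monthly contacts (section 2(a), Monthly Follow-ups); at least 60% major relapse within 6 months (section 1(b), a background figure rather than a design assumption). The documents state no effect size, alpha, power or loss rate, so there is no figure of the plan's own to reproduce.

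**Step 1. The passages side by side.**

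| Hypothesis | Outcome | Model |
|---|---|---|
| Primary 1b | Duration of abstinence | Cox |
| Secondary | Duration of abstinence | LMM or GLMM |
| Exploratory 1b | Duration of abstinence | Cox |
| Exploratory 2b | Duration of abstinence | Cox |

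**Step 2. How many durations are incomplete.** With no loss, the number censored at 6 months is 40 × (1 − relapse rate). At 60% this is 40 × 0.40 = 16. At 50% it is 20 and at 80% it is 8.

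**Step 3. What the mixed model becomes.** With one duration per participant, a random intercept cannot be separated from the residual, so the Gaussian mixed model reduces to ordinary regression. In the simulations, ordinary regression on observed duration stands for the LMM branch and a Gamma model with log link for the GLMM branch.

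**Step 4. Simulated power for the interaction.** Assumptions: 20 per arm; 182 days of follow-up; sham relapse 60%; active hazard ratio 0.6; imaging log hazard ratio 0.6 or 1.0 per SD in the active arm only; loss unrelated to imaging. At average imaging values, the share reaching 6 months is 0.40 in sham and 0.40^0.6 = 0.577 in active. The mean is 0.49, which leaves about 40 × 0.51 ≈ 20 relapses. All models adjust for age. Linear and Cox cut-offs were set so that each rejects 5% under the null. The core settings (0% and 20% loss) used 20,000 trials each.

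| Loss | Log HR per SD | Linear | Gamma | Cox |
|---|---|---|---|---|
| 0% | 0.6 | 17% | 15% | 23% |
| 0% | 1.0 | 35% | 36% | 49% |
| 10% | 1.0 | 29% | – | 43% |
| 20% | 0.6 | 12% | 12% | 20% |
| 20% | 1.0 | 26% | 28% | 44% |

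Without calibration, the size was 5.0–5.1% for linear, 6.1–6.4% for Gamma and 6.2–6.3% for the Cox Wald test. At 20% loss, 14% of durations are drop-out dates, and the linear slope shrinks from −33.7 to −29.5 days per SD, about one eighth. Excluding drop-outs instead steepens the slope by about 4%, with power of 14% and 30%.

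**Step 5. Sensitivity of the gap (linear vs Cox).**

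- Sham relapse 75%, no loss: 21% vs 27% and 43% vs 56%.
- Log-normal times, no loss: 18% vs 20% and 36% vs 44%. Log-logistic: 17% vs 20% and 33% vs 43%. With 20% loss at the larger effect: 29% vs 43% and 27% vs 40%.
- A separate log-normal simulation with regression on log duration, at nominal 5%: 25% vs 28% and 67% vs 71% with no loss; 17% vs 27% and 49% vs 67% with 20% loss.
- Relapse dated only to the monthly contact, no loss, log HR 1.0: 33% vs 45%.
- Imaging effect in opposite directions in the two arms, no loss: 48% vs 52% in one run and 44% vs 51% in another.
- Alpha divided by three for three imaging measures (assumed strictest step), no loss: 8% vs 11% and 20% vs 31%.

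**Step 6. Drop-out that depends on imaging.** With no true effect, 20% loss, and drop-out depending on imaging in the active arm, the rejection rates at nominal 5% were:

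| Dependence (log HR per SD) | Linear | Cox | False linear slope (days per SD) |
|---|---|---|---|
| 0.3 | 5.8% | 6.8% | 3.9 |
| 0.5 | 6.1% | 6.7% | 6.5 |
| 0.7 | 7.6% | 6.7% | 9.6 |
| 1.0 | 10.1% | 6.3% | 14.8 |

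Where such drop-out opposes a true log HR of 1.0, linear power (uncalibrated) falls from 27% with no dependence to 22%, 18% and 10% at dependence of 0.3, 0.5 and 1.0. Cox stays at 47–50%.

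**The case against.** - **A GLMM can handle censoring.** Fitted to monthly relapse indicators it is a discrete-time hazard model, and the monthly contacts would supply the data. That is true of the model class. It does not fit this text, which makes duration the response and lets its distribution choose the model.
- **A duration capped at 6 months is a legitimate outcome.** Read that way, an abstainer's 6 months is a complete observation and the linear test is valid. This stands for complete follow-up, where the cost is power alone. The SAP does not define such an outcome, and drop-outs would still need a rule.
- **Loss may be low.** Contacts can be by telephone (section 2(a)), each monthly contact is paid and there is a completion bonus (section 8(k)), and participants withdrawn after a seizure stay in assessments (section 9(c)). Participants may, however, withdraw at any time (section 13.1). The 20% loss figures are therefore illustrative, and the no-loss rows are the safer guide.
- **The larger gaps favour Cox by construction.** This stands in part. They come from proportional-hazards data with an imaging effect in the active arm only. The SAP's own rationale, that these deficits raise relapse risk, suggests an opposite slope in sham, which cuts the no-loss gap to 4 to 7 points.
- **The Cox Wald test is slightly oversized at about 20 events.** This also stands. Inflation of the linear test beyond Cox's own needs strong imaging-dependent drop-out.
- **The documents do not say that exact relapse dates are recorded.** Correct, but Primary 1b has the same need, and the gap persists with monthly dating.

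**Conclusion.** The concern holds and should be fixed. As written, the Secondary Hypothesis uses a model with no provision for censoring on an outcome that the SAP elsewhere treats as time to event. Under the assumed effects, the cost with no loss ranges from about 2 to 14 points of power across the data models tried. It grows with loss: 18 points (26% against 44%) in the main model at 20% loss and the larger effect. The estimate is distorted only when there is loss. The GLMM branch does not close the gap.

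The test is underpowered under either method, so the change does not rescue it; it stops the analysis from discarding information. Primary 1a and 1b are not affected. The missing censoring rule is common to all the SAP's Cox paragraphs; what is particular to this hypothesis is the model class.

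**What to change.** Replace the model with Cox regression of time from the final session to relapse, containing treatment, the imaging measure, their interaction and age. Censor participants without relapse at the last completed contact or at 6 months, whichever comes first. State the same rule for Primary 1b and Exploratory 1b and 2b. Say how a relapse between contacts is dated, in the same way for all four analyses. Keep the separate model for each imaging measure and the modified Bonferroni procedure, and report the hazard ratio per SD in each arm with its 95% confidence interval.

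As an option, add a p-value from permuting the imaging measure within arm, because the Wald test runs at 6–7% here. Its simulated size was 4.7%, and its power was 44% against 50% for the Wald test at log HR 1.0 with no loss (1,000 trials with 99 permutations each).

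The cost is SAP wording. The relapse and last-contact information is the same as Primary 1b already needs. The only downside is the lower nominal power of the optional permutation test.
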